## 12. ADVERSE EVENTS

### 12.1. GENERAL INFORMATION

Adverse event (AE): any untoward medical occurrence associated with the use of a drug in humans, whether or not considered drug related. AEs include any new events not present during the pre-intervention period or events that were present during the pre-intervention period, which have increased in severity.

All adverse events that occur during the course of the study will be recorded in the source documentation including the event's onset and resolution date (if the event has resolved), the frequency and severity of the event, a summary of any action taken as a result of the event (both in regard to any treatment given and to any change in dosing with the test medication), and an assessment of the event's relationship to the test medication.

### 12.2. NON-SERIOUS ADVERSE EVENTS

A nonserious adverse event is an adverse event that does not meet the requirements for a serious adverse event (see Section 13.3). Nonserious adverse events will be documented in study records and reported to the FDA in the annual IND report. All nonserious adverse events will be recorded in study documentation regardless of whether or not they are considered to be related to the test medication.

### 12.3. SERIOUS ADVERSE EVENTS

Life threatening AE: Any AE that places the subject, in the view of the investigator, at immediate risk of death. It does not include an adverse event or suspected adverse reaction that, had it occurred in a more severe form, might have caused death.

Serious Adverse Event (SAE): Any adverse event that, in the view of the investigator, results in any of the following outcomes:

- Death
- A life-threatening adverse event
- Inpatient hospitalization
- A persistent or significant incapacity or substantial disruption of the ability to conduct normal life functions
- A congenital anomaly/birth defect

Important medical events that may not result in death, be life-threatening or require hospitalization may be considered serious when, based upon appropriate medical judgment, they may jeopardize the subject and may require medical or surgical

intervention to prevent one of the outcomes listed in this definition. Examples of such medical events include allergic bronchospasm requiring intensive treatment in an emergency room or at home, blood dyscrasias or convulsions that do not result in inpatient hospitalization, or the development of drug dependency or drug abuse.

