## 12.4 REPORTING OF SERIOUS ADVERSE EVENTS

### 12.4.1. Reporting to FDA

For serious adverse events (SAE), a MedWatch Form FDA 3500A containing all available information must be sent to the FDA within 15 days of the Investigator's knowledge of the event; new information should be reported by telephone or fax as soon as it becomes available. Fatal or life-threatening SAEs will be reported to the FDA within 7 days of the Investigator's knowledge of the event. We will also inform Pfizer, the manufacturer of sildenafil (Revatio®), about the SAE. SAEs at any given site will be communicated to Stanford immediately by phone or email and reported to the FDA by Stanford on the timelines described above. All coordinating sites will be informed of SAEs promptly.

A MedWatch Form FDA 3500A must be completed for all serious adverse events and forwarded to the FDA within 15 days of the Investigator's knowledge of the event and to the Institutional Review Board/Independent Ethics Committee, according to their requirements. When new significant information is obtained as well as when the outcome of an event is known, the Investigator must inform FDA by telephone or fax. Fatal or life-threatening SAEs will be reported to the FDA within 7 days of the Investigator's knowledge of the event

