#### **12.4.3. Reporting to DSMB**

Reporting to the DSMB is described in detail in the Safety Monitoring Plan, under Item 10, section 2 of the IND application. In brief, SAEs will be reported as soon as possible to the DSMB Safety Officer, who will determine if it is necessary to convene the entire DSMB, and any other events that are potentially reportable to other regulatory agencies will also be reported to the DSMB.

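### The serious adverse event definition covers hospital admission but not prolongation of an existing stay, so a separate harm in a child already in hospital can be classed as non-serious

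*Combined protocol and SAP*

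**What the plan says.** Section 12.3 defines a serious adverse event as "Any adverse event that, in the view of the investigator, results in any of the following outcomes". Five outcomes follow: death, a life-threatening event, "Inpatient hospitalization", lasting or significant incapacity or substantial disruption of normal functioning, and a birth defect.

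A further paragraph permits, but does not require, other important medical events to be classed as serious. The judgment is a medical one, and it turns on whether the event could endanger the child and call for treatment. The purpose of that treatment is described as "intervention to prevent one of the outcomes listed in this definition".

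Section 12.2 makes every event that fails this test non-serious and gives its route: "Nonserious adverse events will be documented in study records and reported to the FDA in the annual IND report". For a serious event, Section 12.4.1 says that a MedWatch form "must be sent to the FDA within 15 days of the Investigator's knowledge of the event", or within 7 days if the event is fatal or life-threatening. Section 12.4.2 sends all serious events to the IRB within 10 working days. Section 12.4.3 says "SAEs will be reported as soon as possible to the DSMB Safety Officer".

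The class is used in two other places. Section 10.3 summarizes adverse event incidence by seriousness, and Section 4.2 has the treatment code broken when a serious event occurs.

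**The concern.** The hospital criterion asks whether the event led to an admission. An event in a child who is already an inpatient cannot do that, however much longer it keeps the child there. Two children could have the same harm, and only the one who was at home when it began would have it classed as serious on the hospital criterion.

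That classification controls the speed of FDA and IRB reporting, notice to the DSMB Safety Officer, information to the manufacturer and the other sites, the code break, and the row of the safety table in which the event appears. In a placebo-controlled trial in children aged 6 months to 10 years, these should depend on the harm and not on where the child was when it began.

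Hospital stays during the study are plausible. The synopsis allows antibiotics and surgical drainage for infected lesions, and Section 3.1 names infection, bleeding and airway obstruction among the complications of the disease. The protocol does not say that any of these would be managed in hospital.

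**Working it through.** No arithmetic applies, because the point is about a definition and the reporting routes that hang on it. The check has three steps.

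**1. Is prolongation mentioned anywhere?** Sections 10.3 and 12.1 to 12.6, and the rest of the supplied text, were read for it. It does not appear.

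**2. Which events fall through?** Take an event in an admitted child that lengthens the stay, and test it against Section 12.3.

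- *It caused the admission and then got worse.* It is already serious on the hospital criterion. Section 12.4.1 also requires significant new information, and the outcome, to be passed to the FDA. There is no gap.
- *It is fatal, life-threatening, incapacitating or substantially disruptive.* It meets another listed outcome. There is no gap.
- *It is separate from the cause of admission, whether new or already present, and is none of the above.* It meets no listed outcome. It is serious only if the investigator uses the important-medical-event clause. Otherwise Section 12.2 makes it non-serious.

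**3. What follows for the third kind of event?** The table compares it with the same event in a child at home who is admitted because of it.

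| Consequence | Event causes an admission | Separate event lengthens an existing stay, clause not used |
|---|---|---|
| Class (12.2, 12.3) | Serious | Non-serious |
| FDA (12.2, 12.4.1) | Within 15 days | Annual IND report, so up to about 12 months |
| IRB (12.4.2) | Within 10 working days | Within 10 working days only if it is an unanticipated problem, or both unexpected and research-related |
| DSMB (12.4.3, 9) | Safety Officer, as soon as possible | Only if potentially reportable to another agency; otherwise at the general safety review, with meetings at least twice a year |
| Manufacturer and other sites (12.4.1) | Informed | No stated requirement |
| Treatment code (4.2) | Broken | Not broken on this ground |
| Safety summary (10.3) | Counted as serious | Counted as non-serious |

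The FDA row shows the clearest difference, because no other FDA route is stated for a non-serious event. The IRB and DSMB rows show a partial difference, confined mainly to events that are expected or judged unrelated.

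**The case against.** The best reply is that the definition already relies on the investigator's judgment and has two elements that can catch these events. Substantial disruption of normal functioning could be applied to some severe in-hospital events. The important-medical-event clause fits a complication treated to prevent death, a life-threatening state or incapacity, and it fits more clearly the graver the event. This stands as a limit on the size of the gap. It does not close it: the clause is permissive, it refers back to the listed outcomes, and prolongation is not one of them. With up to four centers, two investigators could class the same event differently and both follow the text.

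Three stronger readings are tempting, and the documents do not support them.

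- *Any event that worsens in hospital escapes.* It does not. An event that caused an on-study admission is already serious and carries a follow-up duty to the FDA under Section 12.4.1.
- *The DSMB would never learn of such an event.* Section 12.4.3 also sends it events potentially reportable to other agencies, and Section 9 has it evaluate safety and meet at least twice a year. Delay is possible for some events, but the text does not imply that the board stays unaware.
- *One or two misclassified events would materially change the serious-event count among 60 children.* The documents give neither an expected number of serious events nor a hospitalization rate, so there is nothing to set this against. Sections 5.2 and 5.3 also exclude children with unstable health or currently infected or ulcerated lesions, which may make admissions less common.

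The details of DSMB monitoring and reporting sit in the Safety Monitoring Plan in the IND application, which is not part of these documents. A wider definition of seriousness there cannot be ruled out. If there is one, the protocol would still have to be brought into line with it.

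**Conclusion.** The point holds in a narrow form. As Section 12.3 is written, a separate event that prolongs a hospital stay and meets no other listed outcome is non-serious unless the investigator chooses otherwise. Its stated FDA route is then the annual report in place of a 15-day report. Prompt IRB and DSMB notice is at risk mainly when the event is expected or unrelated.

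This rests on two assumptions: that some children will be inpatients during the study, which is plausible but not stated, and that the Safety Monitoring Plan does not already widen the definition. The number of events affected cannot be estimated from the documents. It is a real gap in a safety rule, of unknown frequency and cheap to close, and it should be corrected. It does not affect the primary efficacy comparison as such.

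**What to change.** In Section 12.3, extend the third bullet so that it covers inpatient hospitalization or prolongation of an existing hospitalization. Use the same definition on the adverse event form and for the seriousness summary in Section 10.3, and check that the Safety Monitoring Plan agrees. In the same edit, correct the references in Sections 12.2 and 12.4.2, which send the reader to Section 13.3 for a definition that stands in 12.3.

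The drafting cost is one phrase in the protocol and one on the form. There are two running costs. Slightly more events will be handled as serious. Each added serious event in the first 20 weeks would also trigger the code break in Section 4.2, which could unblind the subject and physician before the week 20 subject and physician assessments. Section 12.6, on unblinding, mentions only withdrawal for an adverse reaction and the week 20 visit, so Sections 4.2 and 12.6 should be reconciled when the definition is widened. After the planned unblinding at week 20 this cost no longer arises.

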## 12.4 REPORTING OF SERIOUS ADVERSE EVENTS

### 12.4.1. Reporting to FDA

For serious adverse events (SAE), a MedWatch Form FDA 3500A containing all available information must be sent to the FDA within 15 days of the Investigator's knowledge of the event; new information should be reported by telephone or fax as soon as it becomes available. Fatal or life-threatening SAEs will be reported to the FDA within 7 days of the Investigator's knowledge of the event. We will also inform Pfizer, the manufacturer of sildenafil (Revatio®), about the SAE. SAEs at any given site will be communicated to Stanford immediately by phone or email and reported to the FDA by Stanford on the timelines described above. All coordinating sites will be informed of SAEs promptly.

A MedWatch Form FDA 3500A must be completed for all serious adverse events and forwarded to the FDA within 15 days of the Investigator's knowledge of the event and to the Institutional Review Board/Independent Ethics Committee, according to their requirements. When new significant information is obtained as well as when the outcome of an event is known, the Investigator must inform FDA by telephone or fax. Fatal or life-threatening SAEs will be reported to the FDA within 7 days of the Investigator's knowledge of the event

### 12.4.2. Reporting to IRB

Unexpected deaths or life-threatening experiences related to the research must be reported to the IRB within 5 working days from the when the site's PI learns of the event. All SAEs (as defined in section 13.3) will be reported to the IRB within 10 working days from when the site's PI learns of the event.

Unanticipated problems involving risks to participants or others, or Internal Events that are unexpected and related to the research should be reported to the IRB within 10 working days from when the site's PI learns of the event or new information, or receives assessment from monitoring entity.

Additional reportable events include: unanticipated problems (UPs) involving risks to participants or others (including internal or external events, deaths, life-threatening experiences, injuries, breaches of confidentiality, or other problems) that occur any time during or after the research study.

Additional Reportable information:

- New information that indicates a change to the risks or potential benefits of the research, in terms of severity or frequency
- Protocol deviation. Protocol deviations/violations are to be reported only if:
  - Intended to eliminate apparent immediate hazard to a research participant, or
  - Harmful, or
  - Possible serious or continued noncompliance
- Complaint that is unresolved by the research team, or that indicates increased or unexpected risks
- Incarceration when, in the opinion of the PI, it is in the best interest of the participant to remain on the study

#### **12.4.3. Reporting to DSMB**

Reporting to the DSMB is described in detail in the Safety Monitoring Plan, under Item 10, section 2 of the IND application. In brief, SAEs will be reported as soon as possible to the DSMB Safety Officer, who will determine if it is necessary to convene the entire DSMB, and any other events that are potentially reportable to other regulatory agencies will also be reported to the DSMB.

### **12.5. ASSESSMENT OF ADVERSE EVENT SEVERITY, CAUSALITY, AND EXPECTEDNESS**

Unexpected AE: Any adverse event, the specificity or severity of which is not consistent with the risk information described in the Investigator's Brochure.

Severity: Severity of the AE will be determined by the investigator. Severity may be mild, moderate, or severe:

- Mild – An event is mild if the subject is aware of, but can easily tolerate the sign or symptom
- Moderate – An event is moderate if the sign or symptom results in discomfort significant enough to cause interference with the subject's usual activities
- Severe – An event is severe if the sign or symptom is incapacitating and results in the subject's inability to work or engage in their usual activities

In addition, the Investigator will determine if the adverse event is may have been caused by the test product. The following circumstances would be considered to be possibly related:

- A single occurrence of an event that is uncommon and known to be strongly associated with drug exposure (e.g., angioedema, hepatic injury, Stevens-Johnson Syndrome).
- One or more occurrences of an event that is not commonly associated with drug exposure, but is otherwise uncommon in the population exposed to the drug (e.g., tendon rupture).
- An aggregate analysis of specific events observed in a clinical trial (such as known consequences of the underlying disease or condition under investigation

or other events that commonly occur in the study population independent of drug therapy) that indicates those events occur more frequently in the drug treatment group than in a concurrent or historical control group.

In source documentation, causality will be recorded using the following definitions:

- Not Related – An event is considered to be not related to the use of the test medication when the event is DEFINITELY UNRELATED or UNLIKELY to have any relationship to the use of the test medication
- Possibly Related – An event is considered to be possibly related to the use of the test medication when there is a REASONABLE POSSIBILITY that the test medication caused the adverse event

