## 5.2. INCLUSION CRITERIA

Subjects will be considered qualified for enrollment if they meet the following criteria:

1. Legally authorized representative of subjects willing and able to give consent. Assent will be obtained for subjects between the ages of 7 and 10 years old.
2. Subjects will need to be 6 months of age to 10 years of age at the time of entry into the study.
3. The minimum weight of a subject will need to be 8 kg at the time of enrollment.
4. Subjects will be required to have the clinical diagnosis of lymphatic malformation that appears to be over 3 cm in greatest diameter in order to be evaluated for entry. A review of a previous MRI examination may help confirm the entry criteria on subjects selected to come to Stanford for the MRI screening. The MRI must be performed within six (6) months of the screening visit if used as a baseline measure.
5. The lymphatic malformation should be causing enough disability for the subject requiring them to consider systemic therapy.
6. Females must not be pregnant or breast-feeding.
7. Female subjects of childbearing potential have negative urine-pregnancy test results.
8. A parent or legally authorized representative must be willing and able to ensure subject is present for all required study visits.
9. A parent or legally authorized representative must be able to follow instructions.
10. During the initial screening evaluation portion of the trial the subjects MRI examination will be required to confirm that the lymphatic malformation is present and is greater than 3 cm in diameter in order for the subjects to receive medication. MRI of less than six months is valid to use during screening with the discretion of the study radiologist.
11. Subjects will have no contraindications for the use of sildenafil.
12. Subjects will have a normal eye examination.
13. Subjects will have normal liver and kidney function.
14. Subjects will have no contraindication to MRI examinations such as metal implants, etc.
15. Subject must not be a smoker.

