## **6. STUDY DESIGN**

### **6.1. STUDY DESIGN**

**Figure 6.1-1: Study Design Schematic.** Decision points are indicated in bold text. Treatment periods are indicated. Double lined boxes indicate visits that will occur at the subject's closest site, whether at Stanford or at a Cooperating Research Site (Denver, Chicago, Kansas City).

CLINICAL PROTOCOL – Confidential

This will be a double blind placebo controlled trial with a ratio of 2 sildenafil subjects to 1 placebo subject in the Initial Treatment Period. Sildenafil or placebo will be given for 20 weeks.

60 research subjects will be enrolled.

There will be visits at Screening, Initial dose visit (includes a 2 hour observation period after initial dose), 4 weeks, 12 weeks, 20 weeks and 32 weeks visits. MRI examination will be part of the screening visit and will be repeated prior to the completion of medication at the 20 week visit. For subjects identified at Stanford, all visits will be conducted at Stanford University Medical Center. For subjects identified at other sites, all Screening, Initial Dose Visit, and Week 20 visits will be conducted at Stanford, including both MRIs. All other visits (weeks 4, 12, 32) will be conducted at the subject's local site. These subjects will be given the option to have the blood work for Screening done at their local site or at Stanford. They will also be given the option to have the eye exams and hearing exams at Screening and Week 20 done at their local site or at Stanford. Having these tests done locally at screening may make it easier to re-test if there is a change in vision or hearing while on sildenafil.

At the completion of 20 weeks of medication or placebo the subject will be evaluated by MRI, and will undergo an eye exam and a hearing exam. After the MRI, eye exam, and

hearing exam are completed, the subject will be evaluated by the investigator, and the subject will complete the self evaluation of response. The Investigator will complete the physician evaluation forms. After these evaluations are completed, the blind will be broken and the investigator and subject will know if the subject received placebo or sildenafil. The subject will also be informed of the of the MRI results of the screening MRI and the 20 week MRI once that report is available. Subjects who received placebo for the first 20 weeks will then have the option of starting 20 weeks on active drug.

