### **10.3. SAFETY**

All subjects who receive study medication will be evaluable for the safety analysis. Summary statistics will be provided with respect to patients requiring discontinuation from treatment and from study (any reason and for safety reasons). AE summaries will focus on treatment-emergent AE and will summarize subject AE incidences by severity, seriousness, and relationship to treatment. Vital signs, laboratory tests, and concomitant medication usage will be displayed as listings by subject.

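### The adverse event severity scale has no grade for silent test findings, so the severity table can understate laboratory, blood pressure, eye and hearing harms

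*Combined protocol and SAP*

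**What the plan says.** Section 12.5 of the combined protocol and SAP gives the grading to the investigator and sets three levels: "Severity of the AE will be determined by the investigator. Severity may be mild, moderate, or severe". They are defined as follows.

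- The lowest level is worded: "An event is mild if the subject is aware of, but can easily tolerate the sign or symptom".
- For the middle level the wording is: "An event is moderate if the sign or symptom results in discomfort significant enough to cause interference with the subject's usual activities".
- To reach the top level, the event has to be one that is "incapacitating and results in the subject's inability to work or engage in their usual activities".

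Section 10.3 carries the grade into the analysis: the adverse event summaries "will summarize subject AE incidences by severity, seriousness, and relationship to treatment". The same section presents vital signs and laboratory tests as by-subject listings and does not mention eye or hearing results.

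The scale is applied to children. Section 5.2 states: "Subjects will need to be 6 months of age to 10 years of age at the time of entry into the study". Section 6.1 expects that vision or hearing might change on treatment: it offers local eye and hearing tests at screening because this "may make it easier to re-test if there is a change in vision or hearing while on sildenafil".

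**The concern.** Safety is a stated objective (Sections 2 and 3.3), and much of the planned safety assessment consists of measurements rather than complaints. A scale built only on what the subject notices, suffers or can no longer do has no place for a measured change that causes none of these.

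What is at stake is the one summary meant to show how bad the harms were. A liver enzyme rise, a fall in blood pressure or a hearing threshold shift that the child does not feel could not appear there as moderate or severe, however large. Investigators at up to four centers would also have to settle such cases without a common rule, which could make grades inconsistent.

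**Working it through.** The plan gives no figure to reproduce, and the point rests on wording. The only arithmetic is a count of what is measured.

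**1. Can a silent finding be an adverse event?** Yes. The definition in Section 12.1 covers any untoward medical occurrence and does not require a symptom.

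**2. Can this trial detect one?** Yes, by scheduled tests:

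| Measurement | When | Where stated |
|---|---|---|
| Laboratory: 11 blood count + 16 metabolic panel = 27 items | Screening and Week 20 | 7.4.5, 17.1 |
| Eye examination | Screening and Week 20 | 7.1.6, Table 16-1 |
| Hearing examination | Screening (repeated later if unsuccessful) and Week 20 | 6.1, 7.1.6, Table 16-1 |
| Blood pressure and other vital signs | Every 30 minutes for 2 hours after the first dose (120/30 = 4 sets), and at clinic visits | 7.1.3, Table 16-1 |

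**3. Apply the three definitions to a finding without symptoms or lost function.**

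| Level | What it requires | Met by a silent finding? |
|---|---|---|
| Severe | Incapacity and inability to carry on activities | No |
| Moderate | Discomfort that interferes with activities | No |
| Mild | The subject is aware of it and tolerates it easily | Not literally, because there is no awareness |

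Mild is therefore the most that the rule could give, and on a strict reading it gives no grade. The size of the change enters none of the three definitions.

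**4. Is there another grading rule?** The protocol and SAP contain no toxicity scale and no severity thresholds for laboratory values, blood pressure, hearing or eye findings.

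**5. Where does the grade go?** Into the Section 10.3 summary by severity. Laboratory and vital-sign values appear otherwise only as listings. Eye and hearing results have no planned summary or listing in that section, so the adverse event tables are the only planned safety summary in which they would appear.

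**6. Does age matter?** Step 3 uses no age. An enzyme rise that nobody feels is as ungradable in a ten-year-old as in an infant. Age bears on a separate and smaller matter: how usual activities should be read for a child who cannot report.

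**The case against.** The strongest reply is that severity is only one of several routes by which a harm becomes visible. Section 12.3 lets medical judgment class an important event as serious without hospitalization. Section 12.4.3 sends serious events to the DSMB Safety Officer. Section 10.3 also summarizes by seriousness and relationship, reports discontinuations for safety reasons, and keeps laboratory and vital-sign values visible in listings. Section 7.1.3 tells subjects to stop medication and notify the team if they notice a change in vision or hearing. All of this stands, and it limits the consequence. It does not supply a severity grade: seriousness is a separate axis, a large silent change may fall short of it, listings do not compare arms, and the Section 7.1.3 instruction depends on someone noticing.

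Second, the investigator grades, and the definitions refer to signs as well as symptoms. That is true, but each sign must still be felt or cost function to receive a grade, and no rule is given for departing from the wording.

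Third, lost activity can be observed by a caregiver or examiner, and the reference to work is followed by an alternative that fits children. This also stands: for symptomatic events the scale needs only clarification.

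Fourth, eye, hearing and laboratory tests are scheduled only at screening and Week 20, apart from hearing retests. That limits how many silent findings can arise.

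**Conclusion.** The point holds for severity grading: Section 12.5 cannot grade a silent test finding moderate or severe whatever its size, and read literally does not grade it. Because Section 10.3 tabulates by this grade and plans little else for these data, the severity table can understate such harms. The range of data concerned is clear (27 laboratory items, plus eye, hearing and vital-sign findings), but the number of events is not; the documents give no basis for estimating it.

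Three stronger readings are tempting and are not supported.

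- A reader might infer that silent findings will be tabulated as mild. The text gives them no grade and leaves the investigator to decide.
- A reader might infer that a serious signal would be hidden. Section 12.3 and the listings remain open routes.
- A reader might infer that the defect belongs to the youngest children and measure it by their share of enrolment. It exists at any age, so such a share would not measure it.

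The conclusion assumes that no grading scale applies from outside these documents. The Safety Monitoring Plan cited in Sections 9 and 12.4.3 was not available, and Section 12.5 does not refer to it for severity. If it contains such a scale, a cross-reference may settle the matter.

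**What to change.** In Section 12.5:

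- Keep the three levels for symptomatic events. State that for young children usual activities means feeding, sleep, play or school as observed by a caregiver or examiner.
- Grade test-detected findings by size of change from the screening value. Use one published, age-appropriate toxicity table, named before the first interim look (after 15 subjects, Section 11) and mapped to the same three levels.
- Where that table has no eye or hearing criteria, fix size-of-change categories in advance.
- For hearing, use the first satisfactory test if the screening test failed, and flag it if it was obtained after dosing.

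In Section 10.3, use these grades in the severity summary, by arm.

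For events already recorded, derive the grade mechanically from the recorded values, or have it assigned by someone blinded to treatment. Subjects and investigators are unblinded at Week 20, so open regrading could bias the comparison between arms.

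The cost is protocol and form wording plus the regrading work. Test-based grades use values already being collected. Some events will receive a higher grade than they would now.
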